#### 8.1.1 DEFINITION OF ADVERSE EVENTS (AE)

**Adverse Event:** An AE, as defined by the NIH, is any unfavorable changes in health, including /abnormal laboratory findings that occur in trial participants during the clinical trial or within a specified period following the trial.

All AEs including local and systemic reactions not meeting the criteria for “serious adverse events” will be captured on the appropriate CRF. In addition, the AE Interview will be completed by the study coordinator during each lab visit (see attachment). For any Adverse events reported, a clinician will evaluate and indicate the severity of the event(s). The AE report form (*Appendix A*) will be completed for any reported AE. The AE form includes the following: what is known about the therapy and previous reported side effects, if the AE occurred in temporal relation to the therapy, whether or not the AE improves or disappears when treatment is stopped, whether the AE is a worsening of baseline symptoms or related to a concurrent medical condition or medication use. Once complete, both of these forms will be given to the PI and the Co-I who will review, comment and sign the forms. Completed forms will be placed in the participant’s folder.

The study coordinator will document any AE occurrence on the AE log (*Appendix B*) which includes information such as the date of the AE, severity, relationship to the treatment (assessed by the PI), actions taken, and outcome(s). The log will be reviewed and initialed by the PI 72 hours after being completed. All AEs occurring during the clinical trial will be documented appropriately regardless of relationship to tACS. All AEs will be followed to adequate resolution and will be graded for severity and relationship to the study treatment. Any medical condition noted at the initial session will be considered as baseline and not reported as an AE.

All AEs will be graded for severity using the following guidelines.

- **Asymptomatic:** the participant is exhibiting no symptoms due to the event; no treatment needed.
- **Mild** Adverse Event– Event results in mild or transient discomfort, not requiring intervention or treatment; does not limit or interfere with daily activities (e.g., insomnia, mild headache).

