#### 8.1.3 DEFINITION OF UNANTICIPATED PROBLEMS (UP)

Unexpected Events (UE) will be recorded on the UE/SAE log (*Appendix D*) and will include information including date of the event, when the study team was informed of this event, event details, when the IRB was notified, and whether the SAE Form was completed. The IRB will be notified of each UE that may occur during the study.

The Office for Human Research Protections considers unanticipated problems involving risks to participants or others to include, in general, any incident, experience, or outcome that meets all of the following criteria:

- Unexpected (in terms of nature, severity, or frequency) given (a) the research procedures that are described in the protocol-related documents, such as the IRB-approved research protocol and informed consent document; and (b) the characteristics of the participant population being studied;
- Related or possibly related to participation in the research
- Suggests that the research places participants or others at a greater risk of harm (including physical, psychological, economic, or social harm) than was previously known or recognized.

If an UE occurs the IRB will be notified and the study will be adjusted as needed to protect the health and safety of the participants. Depending on the nature of the UE, the research protocol, inclusion/exclusion criteria, and informed consent will be changed to reflect the possibility of this event reoccurring. During this time, no new participants will be recruited and the research procedures for currently enrolled participants will be stopped. Each UE will be recorded and reported throughout the study.

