### 8.2.2 RELATIONSHIP TO STUDY AGENT

The PI and Co-I will together determine whether an AE is associated with the study treatment. The event will be labeled associated if the event is temporally related to the administration of the therapy and no other factors can explain the event. The event will be labeled as not associated if the event is temporally independent of the study treatment and can be explained by external factors such as major life events.

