#### 8.5 STUDY HALTING RULES

If a seizure or any other Grade III adverse event occurs at the time of a study visit, a temporary hold will be placed over the study and further investigation will ensue. This could lead to stopping the study prematurely or continuing on with further safety measures in place. If it is found after investigation that the seizure was not related to the stimulation then the temporary hold of the study will be lifted. If, after investigation into the seizure or Grade III adverse event occurs, and there is found to be further well tested and documented safety measures that can be employed in the study to prevent further seizures or Grade III adverse events, then the temporary hold on the study will be lifted. If two seizures are witnessed during the study visits, the entire study will be stopped prematurely. These individuals would be referred for further medical attention. It is very unlikely that a seizure will occur, given that previous studies using tDCS in patients with depression and schizophrenia and previous studies in the lab using tACS (IRB14-1622, IRB14-3285) have had no seizures occur (Berlin et al., 2013, Brunelin et al., 2012). The study will also be stopped if other studies provide evidence that transcranial current stimulation has been associated with other, previously unrecognized, potentially harmful effects, either short-term or long-term.

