#### 8.6 SAFETY OVERSIGHT

Safety oversight will be under the direction of a DSMB composed of [name], an epidemiologist, a biostatistician and one or more clinical researchers. The DSMB will review AEs every 6 months whereas the medical monitor will review AEs in real time and make decisions as to each participant's continuation in the trial.

The PI will review AEs weekly with research team and may request additional review by Co-I on a case-by-case basis. The medical monitor will also be present at weekly meetings in order to discuss/explain any event(s) that may occur.

Every 6 months DSMB will review blinded AE reports. If there is reason to view unblinded information, the DSMB will directly receive the list of participants' identification numbers from a [name] Lab member, not otherwise associated with this clinical trial. Participant identification number will be displayed in a table according to the four treatment-sequence groups of the study; however the specific treatment regimens of the four groups will not be disclosed. This will allow the DSMB to compare the four treatment groups.

Reasons for stopping the study and asking for further investigation include; decrease in cognitive abilities based on baseline and end of study data (>25% decrease in scores in 2/10 of the first participants or 20% of participants overall.). In addition, as mentioned above, if a seizure occurs during a study visit, the clinical trial will be temporarily be placed on hold for further investigation.

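### The seizure hold and the two-seizure stop cover only seizures at study visits, and the protocol does not say whether case-study sessions are visits

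*Combined protocol and SAP*

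**What the plan says.** Section 8.5 (Study Halting Rules) has two seizure rules.

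- **Temporary hold.** A seizure, or another Grade III adverse event, that occurs at a study visit puts the trial on hold for investigation. If the investigation finds that "the seizure was not related to the stimulation then the temporary hold of the study will be lifted". The hold can also end if tested safety measures that would prevent a recurrence can be added.
- **Permanent stop.** "If two seizures are witnessed during the study visits, the entire study will be stopped prematurely". This rule has no relatedness test.

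Section 8.6 (Safety Oversight) restates the hold with the same limit: "if a seizure occurs during a study visit, the clinical trial will be temporarily be placed on hold for further investigation".

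A pause without a visit limit appears in 8.1.3. After an unexpected event the IRB is notified and the study is adjusted. The section adds: "During this time, no new participants will be recruited and the research procedures for currently enrolled participants will be stopped". Section 8.5 does not refer to 8.1.3.

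Section 7.4.7 describes a case study of up to 4 participants, each with 12 weekly 40-minute active sessions. It does not say where the sessions take place. Section 4.2 describes the case study as assessing at-home maintenance treatment.

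**The concern.** Both rules depend on where the participant is, not on how plausibly stimulation caused the event. As written, a seizure at the sMRI visit would trigger the hold and, if witnessed, count toward the stop, although 7.4.4 describes no stimulation there. A seizure shortly after a participant leaves a stimulation session would do neither.

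The case study makes this sharper. If an at-home session is not a study visit, a seizure during active stimulation itself would fall outside both rules.

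At stake is a pre-stated safeguard, not the estimand, the analysis or the power. If two seizures occurred after sessions and away from the site, the two-seizure stop would not apply. Each pause would depend on how the event was classified, or on discretion.

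**Working it through.** No arithmetic applies. The documents give no seizure rate, and none can be derived from them. The check is whether any other provision does the work of 8.5 for a seizure between visits.

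1. **Is the event captured?** Yes. Section 8.1.1 states: "All AEs occurring during the clinical trial will be documented appropriately regardless of relationship to tACS". The SAE form in Appendix C asks for location and gives home as an example. The gap is therefore in the trigger, not in data collection.
2. **Does 8.1.3 replace the hold?** Probably in practice, but not automatically. Its criteria for an unanticipated problem are that the event is unexpected, at least possibly related to participation, and suggestive of greater risk than was known. Section 2.3.1 names epileptic discharges as a theoretical possibility, so it could be argued that a seizure is not unexpected. Against that, 2.3.1 says this has not been reported in humans, and 8.5 calls a seizure very unlikely. A first off-visit seizure judged possibly related would therefore probably qualify.
3. **Does 8.1.3 replace the stop?** No. It contains no count. It also says the protocol and consent will be revised to reflect that the event may recur, while judging unexpectedness against those same documents. A second seizure could then be called expected in nature, although its frequency might still qualify it.
4. **Does 8.4 halt the trial?** No. It requires reports to the IRB and DSMB within 24 or 48 hours for unexpected, suspected serious reactions. That is reporting.
5. **Does 5.5 stop the trial?** It may, at the investigator's discretion, with no seizure criterion.
6. **Does 8.6 oversight cover it?** The medical monitor reviews events in real time, but to decide on each participant's continuation. Routine DSMB review is every 6 months.
7. **Does 2.3.1 act on it?** Its seizure provision covers the whole course of the study, but the action is a neurology referral for that participant.

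Several provisions therefore reach an off-visit seizure. None is an automatic seizure hold, and none adds to the two-seizure count.

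**The case against.** The strongest reply is that the matter is largely handled already. The 8.1.3 pause is broader than the 8.5 hold, and a second off-visit seizure bears on the count only if the trial resumed after the first had been reviewed. The visit limit also has a rationale: staff witness the event close to stimulation, so the stop needs no adjudication, whereas off-visit seizures would be reported second-hand. This stands as a reason to grade the point low and to be cautious about the stop. It does not justify limiting the hold, because 8.5 already releases the hold when the seizure proves unrelated.

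Four stronger readings are tempting, and the documents do not support them.

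- A reader might infer that the trial would simply carry on after an off-visit seizure. Sections 8.1.3, 8.4, 5.5 and 8.6 show otherwise.
- A reader might contrast the cognitive threshold in 8.6, a more than 25% "decrease in scores in 2/10 of the first participants or 20% of participants overall". There, overall is set against the first participants, not against visits, and the BACS is itself administered only at visits.
- A reader might cite the 8.5 clause that stops the trial for previously unrecognised "potentially harmful effects, either short-term or long-term". That clause concerns evidence from other studies and says nothing about the scope of in-trial triggers.
- A reader might want to count every off-visit seizure that fails the 8.2.2 label, under which an event is "labeled as not associated if the event is temporally independent of the study treatment and can be explained by external factors". That label needs both conditions. Two unexplained seizures days after a session, even in sham participants, could then force termination. Reasonable reviewers would differ on accepting that.

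**Conclusion.** The point holds as a minor one. The text is clear: the hold in 8.5 and 8.6 and the stop in 8.5 are limited to study visits, no section extends them, and the status of case-study sessions is undefined. The conclusion that 8.1.3 would probably pause the trial is a judgement. It assumes that a seizure soon after stimulation would be classed as unexpected, at least possibly related, and suggestive of greater risk.

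No numerical size can be given. A reader might try to gauge it from how long visits last after stimulation ends. The stated visit lengths are mostly approximate, and such figures would show how long the rule applies, not the risk of a seizure.

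**What to change.** In 8.5 and 8.6:

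- Apply the temporary hold to any seizure from first stimulation to end of participation, wherever it occurs, and state that case-study sessions are included.
- Keep the existing release when the seizure is found unrelated to stimulation.
- Cross-reference 8.1.3.
- Keep the two-seizure stop for visit-witnessed seizures as written. Add to its count any off-visit seizure judged related or possibly related to stimulation after the hold investigation. Both categories are already in the Appendix B log.
- Refer seizures of undetermined cause to the DSMB instead of counting them automatically.

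The change is to wording only and needs no new data, since off-visit events are already recorded. It has two costs: a possible extra temporary hold, and a relatedness judgement that could contribute to stopping the trial.

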#### 8.6 SAFETY OVERSIGHT

Safety oversight will be under the direction of a DSMB composed of [name], an epidemiologist, a biostatistician and one or more clinical researchers. The DSMB will review AEs every 6 months whereas the medical monitor will review AEs in real time and make decisions as to each participant's continuation in the trial.

The PI will review AEs weekly with research team and may request additional review by Co-I on a case-by-case basis. The medical monitor will also be present at weekly meetings in order to discuss/explain any event(s) that may occur.

Every 6 months DSMB will review blinded AE reports. If there is reason to view unblinded information, the DSMB will directly receive the list of participants' identification numbers from a [name] Lab member, not otherwise associated with this clinical trial. Participant identification number will be displayed in a table according to the four treatment-sequence groups of the study; however the specific treatment regimens of the four groups will not be disclosed. This will allow the DSMB to compare the four treatment groups.

Reasons for stopping the study and asking for further investigation include; decrease in cognitive abilities based on baseline and end of study data (>25% decrease in scores in 2/10 of the first participants or 20% of participants overall.). In addition, as mentioned above, if a seizure occurs during a study visit, the clinical trial will be temporarily be placed on hold for further investigation.

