## SCHEMATIC OF STUDY DESIGN

At enrollment, the 40 eligible enrollees will be allocated by randomization to four treatment-sequence groups: tACS-tACS, tACS-sham, sham-sham, sham-tACS) (10 participants per sequence). The randomization will be stratified by sex.

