## 10.4 RANDOMIZATION AND BLINDING

### 10.4.1 ENROLLMENT/ RANDOMIZATION/ MASKING PROCEDURES

Participants will be randomized into one of four treatment-sequence groups. The randomization assignment will occur prior to beginning the initial 5 days of stimulation, once the participant has passed the screening sessions. The randomization will be as follows: tACS and tACS, tACS and sham, sham and sham, sham and tACS. This is a double blind study, so neither the participant nor the researcher will know which treatment treatment-sequence group the participant has been assigned to.

A [name] Lab member ([name]) will randomize 40 codes which will be used by the study coordinator and research assistants. These codes will be randomized prior to recruitment of any participants. These codes are directly linked to which treatment regimens the participants receive (sham (S) or 10Hz tACS (A)).

The codes will be randomized using a randomization function available in MATLAB software. A condition will be included so that the same condition will not be assigned to adjacent participants 3 times in a row. The participant randomization will also be stratified on sex, in that separate randomization schedules will be created for each sex. A total of 40 codes will be randomized for each sex because it is possible that there will be, for example, 35 men and only 5 women.

[name] will have no other responsibility in the study other than providing these randomized codes. The master list containing the condition and the codes will be kept solely by [name].

[name] will provide the study coordinators an Excel document with the blinded randomized codes. This document will remain on the secure lab drive. The study coordinator will enter the participant's study ID next to their randomization code on the first day of stimulation.

(The CONSORT Statement notes that "Allocation concealment is a technique used to prevent selection bias by concealing the allocation sequence from those assigning participants to intervention groups, until the moment of assignment." Randomization without allocation concealment is not reliable randomization.)

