### 10.4.3 BREAKING THE STUDY BLIND/PARTICIPANT CODE

This is a double blind clinical trial. The participant and researchers will remain blinded to stimulation conditions through the completion of data collection. In the event of an AE/SAE, the PI will be able to determine the stimulation condition of the participant.

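### Section 8.6 gives the DSMB only four coded sequence groups when it has reason to unblind, and states no route to the regimen key, so that table cannot show whether an imbalance falls on active or sham stimulation

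*Combined protocol and SAP*

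**What the plan says.** Section 8.6 (Safety Oversight) describes two levels of review. The routine level is masked: "Every 6 months DSMB will review blinded AE reports". The second level applies when the board needs more: "If there is reason to view unblinded information, the DSMB will directly receive the list of participants' identification numbers", sent by a lab member who is otherwise outside the trial. The layout is then fixed: "Participant identification number will be displayed in a table according to the four treatment-sequence groups of the study". What lies behind each group stays hidden from the board: "however the specific treatment regimens of the four groups will not be disclosed". The stated purpose follows: "This will allow the DSMB to compare the four treatment groups".

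The groups are given in the Schematic of Study Design: "tACS-tACS, tACS-sham, sham-sham, sham-tACS) (10 participants per sequence".

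Two other places deal with access to the allocation. Section 10.4.1 says "The master list containing the condition and the codes will be kept solely by" one lab member, who has no other study duty. Section 10.4.3 says "In the event of an AE/SAE, the PI will be able to determine the stimulation condition of the participant". Neither describes passing regimen identity to the DSMB.

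**The concern.** The step offered as unblinding is still masked. In a two-arm trial, coded groups hide only the direction of a difference; the contrast itself stays intact. Here the safety question is active v sham within a period, and each side of that contrast is spread over two of the four coded groups. The board is told neither which two belong together nor which pair is active.

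The plan itself raises the question of attribution. Under section 8.5 a study hold after a seizure is lifted if the seizure is found unrelated to stimulation. Section 8.6 lists cognitive decline as a reason for stopping and further investigation. If a group imbalance is what prompts the board to look, the table it receives cannot tell an excess on tACS from a chance excess on sham.

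**Working it through.** The plan gives no figure for the DSMB comparison (no error rate, power or expected event rate), so there is nothing to reproduce. The check is a count of what the table can and cannot identify, followed by an illustration under assumed rates.

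**Inputs from the documents.** Four sequences of 10, N = 40 (Schematic). In section 10.2's notation they are SS, SA, AS and AA, with stimulation-week regimen first and maintenance regimen second.

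**Contrasts that answer the safety question.**
- Stimulation week: (AA + AS) v (SA + SS), 20 v 20.
- Maintenance: (AA + SA) v (AS + SS), 20 v 20.

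**What unlabelled groups leave open.** Call the coded groups W, X, Y, Z.
- Possible assignments to sequences: 4! = 24.
- Ways to split four groups into two pairs: 3. One split is the stimulation-week contrast, one is the maintenance contrast, and the third (AA + SS v AS + SA) is neither. Each accounts for 24/3 = 8 assignments.
- Within each of the two relevant splits, half the assignments (4 of 8) put active on one side and half on the other. Each period's contrast therefore has 3 × 2 = 6 directed possibilities, of which one is true.

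**Direction.** Suppose W and X have 4 events each and Y and Z have none, so the split is 8/20 v 0/20. Fisher's exact two-sided p is 0.0033, and it is 0.0033 again with the sides exchanged. The imbalance is clear; its direction is not in the data supplied.

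**Effect of a code per period.** If each participant carries X or Y for the stimulation week and a separate X or Y for maintenance, the pairing is known. Only direction remains open: 2 possibilities per period, 2 × 2 = 4 overall instead of 24. The key settles the rest.

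**Illustration of the pooling loss.** The documents give no event rates by arm and prescribe no DSMB test, so the rates below are assumptions. Exact power at two-sided 0.05: Fisher for 20 v 20, and Fisher-Freeman-Halton for four groups of 10, two at each rate.

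| Assumed sham v active rate | Pooled 20 v 20 | Four coded groups |
|---|---|---|
| 5% v 15% | 7.0% | 7.1% |
| 10% v 20% | 7.2% | 7.3% |
| 5% v 20% | 17% | 14% |
| 10% v 40% | 49% | 40% |
| 5% v 40% | 72% | 60% |
| 10% v 50% | 74% | 63% |

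All rows assume full enrolment. With 20 participants in all, 5% v 40% gives 24% pooled and 17% in four groups. The loss is nil at small differences and about 9 to 11 points at large ones, and power is low under either display unless the harm is large.

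**The case against.** A reader might infer that the board cannot judge at all whether stimulation causes harm. The documents do not support that, for three reasons.

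- The coded table is not its only evidence. Section 8.4 sends the DSMB individual reports of unexpected, suspected serious adverse reactions within 24 or 48 hours. The adverse event form (8.1.1, Appendix A) records timing relative to therapy, whether the event improves when therapy stops, and other possible causes. The medical monitor reviews events in real time (8.6). In a trial of 40, case-by-case review carries much of the safety work.
- The written stopping counts do not need the code. The two-seizure stop (8.5) and the cognitive criterion (8.6: 2 of the first 10, or 20% overall) count participants regardless of arm.
- The board is not the only body that weighs relatedness or stopping. Section 8.2.2 gives relatedness to the PI and Co-I, section 5.5 puts premature termination in the investigator's opinion, and section 8.5 names no decision-maker for lifting a hold.

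A reader might also infer that the investigator simply knows more than the board. That comparison is not like for like: 10.4.3 concerns one participant's condition after an event, while 8.6 gives a grouping of all participants.

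Finally, masked first review is a legitimate choice, and the power differences rest on large assumed rates.

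All of this limits the point, but it does not remove it. Nothing in 8.4 says that the individual reports carry the regimen, and 8.6 does more than stay silent on the key: it says the regimens will be withheld at the very step meant for unblinding.

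**Conclusion.** The point holds in a limited form. Followed as written, 8.6 leaves the DSMB with a table from which it cannot tell whether an imbalance falls on active or sham, nor which coded groups share a regimen in either period, and no section gives it a further step. This rests on the text and the count of assignments, not on any assumed event rate.

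It does not show that oversight fails altogether; individual reports and the arm-blind stopping counts still work. The power comparison should be read only as illustration, because it depends on assumed rates and full enrolment. The amendment is worth making: the gap concerns safety oversight and the change costs little.

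**What to change.** Amend section 8.6 as follows.

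1. Coded tables may be the DSMB's first look, but with a separate X/Y code for the stimulation week and for maintenance, so that groups sharing a regimen in a period can be pooled.
2. On the DSMB's request, the lab member not otherwise associated with the trial gives the regimen key to the DSMB alone, with adverse events tabulated active v sham for each period.
3. The PI, raters and coordinators do not receive the key or these tables. The individual-participant provision in 10.4.3 is a separate matter and can stay as it is.

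The cost is wording: the code list already exists (10.4.1), and 8.6 already provides for an independent lab member. The small downside is that DSMB members may know the allocation before the trial ends.
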